### Test of the dose response signal

The null hypothesis of a flat dose-response relationship for the percentage reduction in body weight compared to placebo will be tested at a one-sided significance level of 2.5 % against the alternative hypothesis of a dose-response relationship leading to a significant decrease in percent body weight.

Hence, the following null and alternative hypotheses will be tested:

- $H_{01}$ : there is no dose-response relationship for LIK066 given qd (ie the dose response relationship is flat).
- $H_{11}$ : there is a dose-response relationship for LIK066 given qd (ie as dose increases, the percent weight decreases).
- $H_{02}$ : there is no dose response relationship for LIK066 given bid (ie the dose response relationship is flat).
- $H_{12}$ : there is a dose-response relationship for LIK066 given bid (ie as dose increases, the percent weight decreases).

Given that we suspect the dose-response may behave differently between qd and bid regimens based on the data we have seen from the proof-of-concept study LIK066X2201, we define separate sets of the dose-response candidate models for each dosing regimen. In order to preserve the family-wise error rate at one-sided significance level of 2.5 %, the optimal contrasts derived from the model candidate set for each dosing regimen will be individually

[figure not shown]
compared to the critical value derived using a multiplicity adjustment accounts for all tests of comparing LIK066 doses to placebo across regimens simultaneously as described above. The rejection of the null hypothesis for each dosing regimen will be achieved using the maximum test statistic in each dosing regimen from each estimated contrast test in the candidate set.

The candidate models generating the contrast weights are described in [Table 9-1](#) and depicted in [Figure 9-1](#), with the doses used to define parameters of interest being defined as total daily dose.

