**Figure 9-1 Dose-response curve of candidate models (left panel: qd regimen)**

The analysis to derive the test statistics is based on an analysis of covariance (ANCOVA) model with the percent change in body weight from BL to Week 24 as a response variable, treatment (placebo and all LIK066 doses from each regimen), stratum indicator (dysglycemic/normoglycemic/T2DM) and pooled center/region as factors and BL weight as a covariate. As needed, centers will be pooled according to country and region for the purpose of analysis.

The response variable of percent change in body weight from BL to Week 24 used in the above ANCOVA is from an imputed dataset, where the missing Week 24 weight is imputed using the multiple imputation method as described in [Section 9.4.3](#). In order to account for the imputation uncertainty, this ANCOVA model will be repeated for each imputed dataset, which results in a set of least squares (LS) mean estimates for all dose groups for the two regimens and the related covariance matrices. Rubin's rule will be used to combine the multiple sets of LS mean estimates and the related covariance matrices to a single set of LS mean estimates of percent changes of body weight at Week 24 for all dose groups and the related covariance matrix.

The optimal contrasts derived from the candidate model sets will be applied to the combined estimated dose means and covariance matrix to obtain the t statistics for each candidate model in the two regimens and the common critical value  $C_{0.025}$ .  $C_{0.025}$  is the common critical value derived from the reference multivariate t-distribution with the  $12 \times 12$  correlation matrix induced by testing the candidate dose response models with respect to comparing all candidate models in both dosing regimens to the common placebo group.

The intersection hypotheses  $H_{01}$  and  $H_{02}$  will be rejected and the statistical significance of dose-response in body weight reduction is established if the  $\max(t_1, t_2, t_3, \dots, t_{11}, t_{12}) \geq C_{0.025}$ . In other words, the intersecting null hypothesis requires the rejection of either  $H_{01}$  or  $H_{02}$ .

[figure not shown]

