**Table 9-2 Power for detecting a significant dose response signal\***

Dose regimen	Effect size for best dose	SD	Average power**	Minimum power†
qd	5 %	5.5 %	99.99 %	99.98 %
	5 %	6.5 %	99.71 %	99.57 %
	6 %	5.5 %	99.99 %	99.99 %
	6 %	6.5 %	99.99 %	99.98 %

Dose regimen	Effect size for best dose	SD	Average power**	Minimum power †
bid	5 %	5.5 %	99.16 %	95.84 %
	5 %	6.5 %	96.50 %	86.79 %
	6 %	5.5 %	99.90 %	99.43 %
	6 %	6.5 %	99.28 %	96.36 %

\* Assumes 432 subjects in LIK066 and placebo arms with effective sample size of 367 subjects due to an effect of missing data equivalent to 15 % fewer subjects. Calculations were performed using the DoseFinding package in R.

† Power for a significant dose-response contrast test across all scenarios within each regimen in [Table 9-1](#). The candidate model #5 in bid regimen has the lowest power.

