Given that we suspect the dose-response may behave differently between qd and bid regimens based on the data we have seen from the proof-of-concept study LIK066X2201, we define separate sets for the dose-response candidate models for each dosing regimen. In order to preserve the family-wise error rate at one-sided significance level of 2.5%, the optimal contrasts derived from the model candidate set for each dosing regimen will be individually compared to the critical value derived using a multiplicity adjustment accounts for all tests of comparing LIK066 doses to placebo across regimens simultaneously as described above. The rejection of the null hypothesis for each dosing regimen will be achieved using the maximum test statistic in each dosing regimen from each estimated contrast test in the candidate set.

[figure not shown]
The candidate models generating the contrast weights are described in table 2-3 and depicted in Figure 2-1, with the doses used to define parameters of interest being defined as total daily dose.

The analysis to derive the test statistics is based on an analysis of covariance (ANCOVA) model with the percent change in body weight from BL to Week 24 as a response variable, treatment (placebo and all LIK066 doses from each regimen), stratum indicator (dysglycemic/normoglycemic/T2DM) and region as factors and BL weight as a covariate. Centers will be pooled according to country and region for the purpose of analysis.

Table 2-3 Candidate dose-response models in consideration

#	Candidate models for qd regimen	Candidate models for bid regimen
1	E_{max} model: $ED_{50} = 5$ mg	E_{max} model: $ED_{50} = 5$ mg
2	E_{max} model: $ED_{50} = 50$ mg	E_{max} model: $ED_{50} = 50$ mg
3	Sigmoid E_{max} : $ED_{50} = 75$ mg, $H = 3.5$	Sigmoid E_{max} : $ED_{50} = 75$ mg, $H = 3.2$
4	Sigmoid E_{max} : $ED_{50} = 25$ mg, $H = 0.7$	Linear log-dose: null, $c = 0.8$
5	β -model: $\alpha = 0.8$, $\beta = 0.2$, scale = 180	Linear
6	Exponential: $\lambda = 125$	Quadratic: $\delta = -0.007$

Figure 2-1 Dose-response curve of candidate models (left panel: qd regimen)

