The response variable of percent change in body weight from BL to Week 24 used in the above ANCOVA is from an imputed dataset, where the missing Week 24 weight is imputed using the multiple imputation method as described in Section 2.5.3. In order to account for the imputation uncertainty, this ANCOVA model will be repeated for each imputed dataset, which results in a set of least squares (LS) mean estimates for all dose groups for the two regimens and the related covariance matrices. Rubin's rule will be used to combine the multiple sets of LS mean estimates and the related covariance matrices to a single set of LS mean estimates of percent changes of body weight as Week 24 for all dose groups and the related covariance matrix.

The optimal contrasts derived from the candidate model sets will be applied to the combined estimated dose means and covariance matrix to obtain the t statistics for each candidate model in the two regimens and the common critical value $C_{0.025}$. $C_{0.025}$ is the common critical model derived from the reference multivariate t-distribution with the 12×12 correlation matrix induced by testing the candidate dose response models with respect to comparing all candidate models in both dosing regimens to the common placebo group.

The intersection hypotheses H_{01} and H_{02} will be rejected and the statistical significant of dose-response in body weight reduction established if the $\max(t_1, t_2, t_3, \dots, t_{11}, t_{12}) \geq C_{0.025}$. In other words, the intersecting null hypothesis requires the rejection of either H_{01} or H_{02} .

Model averaging to obtain the dose responses for qd and bid dosing regimens

A parametric bootstrap-based model averaging approach will be implemented to obtain the dose response estimates for qd and bid dosing regimens according to the following steps:

1. The parametric bootstrap procedure will draw a sample of mean percent changes in body weight from baseline to Week 24 for all doses (including placebo) from a multivariate normal distribution, with mean and covariance matrix was determined using Rubin's rule, as described earlier. This sample corresponds to the mean response for each dose (including placebo).

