2.7.2.1 Week 24 analysis

Responder analysis

For the responder analysis, a logistic regression model will be performed using the percent decrease in body weight from BL at Week 24 $\geq 5\%$ or $\geq 10\%$ (yes/no) as a response variable, treatment, glycemic stratification factor and region as fixed factors and BL body weight as a covariate, respectively. The Week 24 missing values will be imputed using the multiple imputation method as described in Section 2.5.3. In order to account for the imputation uncertainty, this logistic regression model will be repeated for each imputed dataset, which results in a set of estimated odds ratio and associated 95% confidence intervals for each LIK066 dose vs placebo contrast, for all dose groups and regimens. Rubin's rule will be used to combine the multiple sets of odds ratios and 95% confidence intervals to a single set of odds ratio and its 95% confidence interval of an LIK066 dose vs placebo. Similar analysis by glycemic status stratification factor will be performed to assess the responder rate for each of the subgroups (normoglycemic subjects, dysglycemic subjects and subjects with T2DM).

In addition, subjects meeting the predefined response criteria (percent decrease in body weight from BL at Week 24 $\geq 5\%$ or $\geq 10\%$) will be summarized by treatment for all subjects and by glycemic stratification factor. A Cochran-Mantel-Haenszel-test will be performed to compare each qd or bid dose to the common placebo.

Dose-response relationship by glycemic stratification factor

For the dose-response relationship in normoglycemic subjects, dysglycemic subjects and subjects with T2DM, the dose-response modeling with the same candidate model sets for the

primary variable as described in Section 2.5.2 will be performed on percent change of body weight from BL at Week 24 for these three subsets of subjects separately.

Summary statistics for body weight will be presented by visit and treatment for observed and imputed values by glycemic stratification factor. Figures will be produced to visually show the raw mean percent changes and the adjusted mean percent changes from the dose response modeling by visit over 24 weeks of Epoch 3 for each treatment group by glycemic stratification factor as well.

Other secondary endpoints

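### Single-step testing of the qd and bid hypotheses leaves the second regimen at about 1.3–1.4% one-sided where a closed test would allow 2.5%; power for the primary objective is unaffected

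*SAP*

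**What the plan says.** Protocol 9.4.2 and SAP 2.5.2 give six candidate models to each regimen and state H01 (flat for qd) and H02 (flat for bid) separately. The SAP gives its aim as "In order to preserve the family-wise error rate at one-sided significance level of 2.5" per cent. To that end the contrasts of each regimen "will be individually compared to the critical value derived using a multiplicity adjustment accounts for all tests" of LIK066 against placebo in both regimens. Protocol 9.4.2 says C0.025 "is the common critical value derived from the reference multivariate t-distribution" with the 12×12 correlation matrix.

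The regimen decision is then described in the protocol: "The rejection of the null hypothesis for each dosing regimen will be achieved using the maximum test statistic in each dosing regimen". The intersection is rejected when the largest of the 12 statistics reaches C0.025; the SAP adds: "In other words, the intersecting null hypothesis requires the rejection of either" H01 or H02. Neither document describes a closed or step-down test after that.

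Protocol 9.8 and SAP 3 report power by regimen, count the primary objective as met if either regimen is significant, and note: "The candidate model #5 in bid regimen has the lowest power". SAP 2.7.2.1 repeats the dose-response modelling by glycemic stratum; it "will be performed on percent change of body weight from BL at Week 24 for these three subsets of subjects separately".

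**The concern.** The same critical value does two jobs. It tests the intersection of H01 and H02, where all 12 contrasts must be allowed for. It also tests each regimen alone, where only six contrasts are at issue once the intersection has been rejected. With two hypotheses and one intersection, the closure principle lets each regimen be tested at the full 2.5% in that second step, and every rejection the plan makes is kept.

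At stake is the regimen-level conclusion. The protocol summary says the primary analysis should inform the choice of doses and regimens, both documents expect qd and bid to behave differently, and power is tabulated by regimen. A test of the second regimen that is stricter than error control requires gives up some power for that conclusion, mostly for bid, which has the lower planned power.

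**Working it through.** **Inputs.** Candidate models: Protocol Table 9-1 / SAP Table 2-3, on total daily dose (qd 0, 2.5, 10, 50, 150 mg; bid 0, 5, 10, 50, 100 mg). Arm sizes from Protocol 5.2: placebo 72, top dose of each regimen 72, every other arm 36. N = 432 randomized, 367 effective. Effects 5% or 6%, SD 5.5% or 6.5% (Table 9-2).

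**Method.** Within a regimen, optimal contrast weights are c_i ∝ n_i(μ_i − μ̄), with μ̄ the n-weighted mean of the model. Each statistic is t = Σc_i·m_i / (s·√(Σc_i²/n_i)), with m_i the arm means, shared placebo and N − 9 degrees of freedom. Critical values are the 97.5% quantiles of the simulated maximum; powers are simulated. Where both regimens are active, qd follows Emax with ED50 = 50 mg.

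**Step 1: the printed table.** For bid, 5%, SD 6.5%, the documents print an average of 96.50% and a minimum of 86.79%. With the 12-contrast value, 432 analysed and each curve's maximum taken over 0–150 mg/day, the rebuild gives 96.6% and 87.0%, and all 16 cells agree within 0.2 points. The scaling is inferred from this agreement; the documents do not state it. It means the linear bid shape reaches only 5 × 100/150 = 3.3% at the highest bid dose. With 367 analysed and the same rule, the figures are 93.9% and 80.3%. Using 367 with a six-contrast value also comes near (minimum 86.4%) but fits less well elsewhere (95.2% against the printed 95.84% for bid, 5%, SD 5.5%).

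**Step 2: critical values.** Twelve contrasts: 2.49. Six qd contrasts: 2.21. Six bid contrasts: 2.25. The one-sided level of a regimen's maximum tested at 2.49 is about 1.3% for qd and 1.4% for bid.

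**Step 3: error control of the closed test.** The closed test rejects H02 if the maximum of all 12 is at least 2.49 and the bid maximum is at least 2.25; H01 likewise with 2.21. Since 2.49 exceeds both, any regimen rejected under the plan is also rejected here.

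| Truth | Error as planned | Error, closed |
|---|---|---|
| Both regimens flat (any rejection) | 2.5% | 2.5% |
| qd active, bid flat (bid rejected) | 1.4% | 2.5% |
| bid active, qd flat (qd rejected) | 1.3% | 2.5% |

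**Step 4: power, SD 6.5%.**

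| Scenario | Analysed | Claim | Planned | Closed |
|---|---|---|---|---|
| Bid linear, 5%, scaled over 0–150 mg/day | 432 | bid | 86.9% | 91.4% |
| Same | 367 | bid | 80.3% | 86.3% |
| Average of six bid shapes, same scaling | 367 | bid | 93.9% | 96.1% |
| Bid linear, 5% at top bid dose | 367 | bid | 99.2% | 99.6% |
| Least favourable bid shape, 5% reached within bid range | 367 | bid | 97.7% | 98.7% |
| Bid linear, 5%, scaled over 0–150 mg/day | 367 | either regimen | 99.6% | 99.6% |

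The shape giving 97.7% is the quadratic, which peaks at 1/(2 × 0.007) = 71 mg/day, between two bid arms. Gains for qd are at most 0.6 points in the planned scenarios.

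**Step 5: illustrations outside the plan's scenarios.** These use assumed values. With a 3% effect reached within the bid range (bid linear) and 367 analysed, bid power goes from 70.5% to 75.7%, and power for both regimens from about 53% to 64%. In one stratum of 432/3 = 144, with no loss and 5% reached within the bid range, power for both goes from 57.8% to 68.4%; with the 0–150 scaling, from 31.4% to 41.0%.

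**The case against.** The plan promises 2.5% family-wise and delivers it; it never promises 2.5% per regimen. A reader might infer that study power is being lost. It is not: either regimen meets the primary objective, and that probability depends only on the intersection test, which would not change.

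A reader might also infer that target dose selection hangs on the second test. Protocol 9.4.2 bases target doses on model-averaged estimates, and the averaging in SAP 2.5.2 is a bootstrap with gAIC selection that is not gated on contrast significance. A regimen that misses significance is still modelled. Protocol 9.4.2 does select models by contrast significance, so that text needs care if the rule changes.

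The gain of 4 to 6 points depends on the 0–150 mg/day scaling. That scaling fits the printed table, but no bid arm receives 150 mg/day. If the best dose lies within the bid range, as the table's label suggests, the gain is about one point or less. The 3% effect is not a planned scenario, and rejecting both regimens within a stratum is not a planned claim.

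All of this stands and limits the size of the point. What does not stand is a defence of single-step testing as the price of simultaneous confidence limits: the SAP reports bootstrap percentile intervals and makes no use of such limits.

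**Conclusion.** The point holds as lost efficiency. The planned procedure is valid, but stricter than it need be for whichever regimen is second: about 1.4% for bid or 1.3% for qd, where 2.5% is available at the same family-wise error. The benefit of closure is confined to the second-regimen claim and the claim for both. In the planned scenarios under the scaling that reproduces the printed table, bid minimum power gains between 0.3 and 6.0 points. It is under one point for the linear shape if 5% is reached at the top bid dose, and about 10 points for both regimens under the illustrative smaller effect or within one stratum.

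The figures assume planned arm sizes, equal variance and complete data; the covariance pooled by Rubin's rule would shift the critical values slightly. The documents do not support reading this as an inflated error rate, a loss of power for the primary objective, or a flaw in how target doses are derived.

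**What to change.** In SAP 2.5.2 and Protocol 9.4.2, keep max(t1, …, t12) ≥ C0.025 from the 12×12 matrix as the test of the intersection. Add that, only if it rejects, H01 is tested by the qd maximum against the critical value from the 6×6 qd matrix and H02 by the bid maximum against the value from the 6×6 bid matrix. Use the same rule by stratum in SAP 2.7.2.1. In Protocol 9.4.2, either state which critical value governs model selection for the averaging or align that text with the SAP's gAIC approach. Restate the regimen-level powers in Protocol 9.8 and SAP 3, with the number analysed and the effect scaling given.

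The cost is some text and two further critical values from the same software, with no added patients. The protocol change needs an amendment under Section 11.1. Timing matters: it must be specified before the Week 24 unblinding. The SAP supplied is Amendment 2 of August 2018, and its document history for May 2018 already refers to Week 24 results. Relaxing the second-regimen threshold in that version would change the primary test after results were known, and the error control shown above could not then be claimed.

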2.5.3 Handling of missing values/censoring/discontinuations

Missing data for the primary endpoint will be imputed using a multiple imputation approach that assumes that the missingness mechanism can be retrieved from observed data (missing at random; MAR). The imputation model will be fitted within each treatment and stratum, using MCMC method, based on the longitudinal sequence of body weight data collected at each visit up to and including Week 24.

2.5.4 Supportive analyses

As a sensitivity analysis, the dose-response modeling as described in Section 2.5.2 will be conducted in the PPS as well. In addition, the same dose-response modeling will be conducted in the FAS using on-treatment weight data only. On-treatment data refer to those collected during the double-blind period, and prior to or within 7 days of the final study medication intake date in Epoch 3.

Summary statistics for body weight will be presented by visit and treatment for observed and imputed values. The summary statistics n, mean, standard deviation, median, minimum, maximum, Q1 and Q3 will be presented for the BL values and similarly for absolute values at post-BL and percent changes from BL to the post-BL visits. Summary statistics for body weight will also be presented by visit and treatment for observed values by subgroups of interest: age group, gender, BMI categories and region.

Figures will be produced to visually show the raw and the imputed mean percent changes as well as the estimated mean percent changes from the dose response modeling by visit over 24 weeks of Epoch 3 for each treatment group.

In addition, the individual patients' percent change in body weight from BL at Week 24 will be depicted by waterfall plot as appropriate.

2.6 Analysis of the key secondary objective

There is no key secondary objective for the study.

2.7 Analysis of secondary efficacy objective(s)

2.7.1 Secondary endpoints

2.7.1.1 Week 24 analysis variables

- Responder rates based on percent decrease in body weight from BL at Week 24 $\geq 5\%$, or $\geq 10\%$.
- Dose-response relationship in normoglycemic subjects, dysglycemic subjects and subjects with T2DM after 24 weeks of treatment.

- Change from BL at Week 24 in waist circumference.
- Change from BL at Week 24 in HbA1c.
- Change from BL at Week 24 in FPG.
- Change from BL at Week 24 in SBP and DBP.
- Percent changes from BL at Week 24 in the fasting lipid profile (TG, total cholesterol, high density lipoprotein (HDL) cholesterol, low density lipoprotein (LDL) cholesterol, lipoproteins, calculated very low density lipoprotein (VLDL) cholesterol and non-HDL cholesterol).
- Percent change from BL at Week 24 in hsCRP (\log_{10} transformed).
- Change from BL at Week 24 in 24-h UGE.

2.7.1.2 End of study analysis variables

Changes from Week 24 to study end in each efficacy variable, body weight, FPG, HbA1c, SBP, DBP, lipid parameters, hsCRP (\log_{10} transformed), 24-h UGE and waist circumference.

2.7.2 Statistical model and method of analysis

All analyses on secondary variables will be performed using the FAS.

